6.6.2.2. Vital Signs

Vital sign measurements include temperature, pulse rate, and seated measurement of diastolic and systolic blood pressure. For each patient, temperature should be recorded using the same modality throughout the entire study. Patients should be sitting at rest for 5 minutes before blood pressure is measured. When vital sign measurements are scheduled at the same time as an ECG and blood draw, the vital signs, when possible, will be obtained immediately prior to the ECG and blood draw, and the blood draw will be collected at the scheduled time.

6.6.2.3. Physical Exams and Visual Acuity

A complete physical examination will include head, ears, eyes, nose, mouth, thyroid, skin, heart, and lung examinations, lymph nodes, gastrointestinal, skeletal, and neurological systems. All subsequent physical examinations should focus on signs and symptoms reported by the patient to assess for clinically significant changes from the baseline assessment.

Visual acuity will be evaluated at Screening, Week 25, and Week 49 by a standard visual eye chart. Presenting visual acuity must be assessed with the supplied study eye chart. If the patient uses corrective lenses, he should wear his usual prescription glasses or contact lenses during the assessment, and the same prescription lenses should be worn at subsequent visual testing, as possible. Perform the visual acuity testing using the entire eye chart. Do not stop at a visual acuity of 100 – continue as far as the patient can go per the testing instructions (see the investigator site file for additional details).

Patients whose presenting visual acuity score is 90 or lower at the screening visit should be encouraged to obtain a diagnostic evaluation from an eye care provider (ie, an ophthalmologist or an optometrist). Any findings (ie, diagnoses) from the eye examination should be recorded as medical history.

Patients whose presenting visual acuity score at Week 25, Week 49, or Early Termination has decreased by 10 or more points from the screening visit must be referred to an ophthalmologist for a diagnostic evaluation. A copy of the ophthalmology consultation must be submitted to the sponsor.

6.6.2.4. Clinical Laboratory Samples

All protocol-required laboratory assessments must be conducted in accordance with the investigator site file and the protocol Schedule of Activities (see Section 1.1). Laboratory requisition forms must be completed and samples must be clearly labelled with the patient ID number, protocol number, site/center number, and visit date. Details for the preparation and shipment of samples will be provided. Reference ranges for all safety parameters will be provided to the site by the central laboratory.

The samples collected for clinical laboratory tests are listed in [Table 6-1](#).

Table 6-1 Clinical Laboratory Tests

Hematology	Serum Chemistry	Metabolic Panel
Hematocrit	Albumin	Total cholesterol
Hemoglobin	Alkaline phosphatase	High density lipoprotein cholesterol
Leukocytes with differential	ALT	Low density lipoprotein cholesterol
Neutrophils and absolute neutrophil count	AST	Triglycerides
Platelet (count)	Bilirubin (total) Blood urea nitrogen Calcium Carbon dioxide Creatinine Chloride Serum gamma-glutamyl transferase Glucose Lactate dehydrogenase Magnesium Phosphate Potassium Sodium Urate	Hemoglobin A1c
Endocrine Panel	Diagnostic Screening (investigator's discretion)	
Serum testosterone Serum LH Serum FSH Serum sex hormone binding globulin	Hepatitis panel, according to CDC criteria	

Abbreviations: ALT, alanine aminotransferase; AST, aspartate aminotransferase; FSH, follicle-stimulating hormone; HBsAg, hepatitis B virus surface antigen; HCV, hepatitis C virus; LH, luteinizing hormone

A separate sample will be collected at the Day 1 visit and will be banked and tested for presence of hepatitis A, B, and C (hepatitis A antibody, IgM, hepatitis B core antibody, IgM, hepatitis B surface antigen, and hepatitis C antibody) if requested by the medical monitor for evaluation of abnormal liver function tests.

The central laboratory will perform laboratory tests for chemistry, hematology, and plasma and serum hormone levels.

All laboratory tests with values that are considered abnormal and clinically significant during participation in the study or within 28 days after the last dose of study drug should be repeated until the values return to normal, baseline, or have stabilized. Abnormal and clinically significant results should be reported as adverse events.

6.6.2.5. 12-Lead Electrocardiograms

A 12-lead ECG will be administered at the time points specified in the Schedule of Activities (Section 1.1). When an ECG is scheduled at the same time as vital signs and a blood draw, the ECG, when possible, will be obtained after the vital signs and prior to the blood draw; the blood draw will be collected at the scheduled time. ECGs will be read locally by a qualified physician.

If patients have a prolonged QTcF (> 500 msec), as measured by Fridericia's formula [$QTcF = QT/(RR^{0.33})$], in the absence of a pacemaker, the ECG should be repeated and confirmed. Patients with a confirmed $QTcF > 500$ msec, in the absence of a pacemaker, as read by a cardiologist should be withdrawn. All abnormal ECG findings must be documented by the investigator as clinically significant or not.

6.6.2.6. Concomitant Medications and Procedures

Medications used by the patient and therapeutic procedures completed by the patient 30 days prior to the first dose of study drug until 30 days after the last dose of relugolix or 12 weeks plus 30 days after the last leuprolide acetate injection will be recorded in the eCRF (Exception: amiodarone will be reported if taken within 3 months prior to the first day of study drug). See Section 5.10.1 for a list of medications and therapies that are prohibited and/or allowed during the study.

6.6.2.7. Radiologic Assessment

CT imaging or MRI of the abdominopelvic region with contrast (except where contrast is medically contraindicated) and a bone scan must be obtained prior to randomization for each patient to determine the presence or absence of metastatic disease (metastases in regional lymph node[s] are considered N1 and will, therefore, be stratified as non-metastatic). The scans should be read locally and do not need to be repeated if a scan exists within 60 days prior to the Baseline Day 1 visit. However, if CT or MRI demonstrates presence of metastatic disease, a bone scan is not required. If metastatic disease is not present on CT or MRI, then a bone scan is also required.

Radiologic assessment is not included as part of the Schedule of Activities after randomization.

6.7. Biological Sample Retention and Destruction

Biological samples present at the conclusion of this study may be retained in storage by the sponsor for a period up to 10 years for purposes of this study.

Exploratory testing for markers of cardiovascular disease, including tests such as plasma N-terminal pro-brain natriuretic peptide (NT-proBNP) or markers for ischemia, may be conducted using stored samples from patients who provided consent for this testing, to explore whether there are differences in measures of cardiovascular function between patients treated with relugolix and patients treated with leuprolide, to inform future studies.

Samples of 8 mL of whole blood for pharmacogenomics testing (see Section 6.6.1.3) will be collected. The need to conduct pharmacogenomic analysis may be identified after this study

(or additional studies) has been completed. For this reason, the collected samples will be retained for up to 10 years after the last patient completes the study. A patient may request the destruction of his sample at any time. The sponsor may destroy the samples sooner than 10 years after the study completes.

7. SAFETY CONSIDERATIONS

Study assessments of safety include adverse events, physical examinations including visual acuity assessment, vital signs, weight, ECGs, and clinical laboratory tests.

7.1. Adverse Event Definitions

7.1.1. Adverse Event

An adverse event is any unfavorable and unintended sign (including an abnormal laboratory finding), symptom, or disease (new or exacerbated) temporally associated with the use of a medicinal product, whether or not related to the medicinal product.

Events meeting the definition of an adverse event **include**:

- A worsening, excluding minor fluctuations, in the nature, severity, frequency, or duration of a pre-existing condition;
- Development of an intercurrent illness during the study;
- Development of symptoms that may or may not be related to the use of a concomitant medication or investigational product;
- Injury or accidents: If a medical condition is known to have caused the injury or accident, the medical condition and the accident should be reported as 2 separate medical events (eg, for a fall secondary to dizziness, both “dizziness” and “fall” should be recorded separately); and
- An investigational abnormality (eg, laboratory parameter, vital sign, ECG) only if the abnormality is considered clinically significant by the investigator based on at least one of the following criteria:
 - Induces clinical signs or symptoms;
 - Requires active intervention; or
 - Requires interruption or discontinuation of study drug.

Events that **do not** meet the definition of an adverse event include:

- Medical or surgical procedures (eg, surgery, endoscopy, tooth extraction, transfusion); the condition that leads to the procedure is an adverse event;
- The disease/disorder being studied, or expected progression;
- Pre-existing diseases or conditions present or detected before the start of study drug administration that do not worsen; and
- Situations where an untoward medical event has not occurred (eg, planned hospitalization for an elective procedure, with elective defined as known or planned at the time of signing of the informed consent).

Adverse events that occur during the study should be evaluated by the investigator and graded according to CTCAE ([Appendix 5](#)). Episodic adverse events, such as vomiting, or those that occur repeatedly over a period of consecutive days are “intermittent”. All other events are “continuous”. Additional information on detecting, documenting, and reporting adverse events and serious adverse events are provided below. No toxicity-related dose reductions of study drug are permitted; however, study drug can be held for a period of up to 10 days for evaluation and treatment of an adverse event. The study drug may be restarted if deemed safe for the patient by the investigator.

7.1.2. Serious Adverse Event

A serious adverse event is any untoward medical occurrence that, at any dose:

- a. Results in death;
- b. Is life-threatening;

NOTE: The term “life-threatening” in the definition of “serious” refers to an event in which the study patient was at risk of death at the time of the event. It does not refer to an event, which hypothetically might have caused death, if it were more severe. For example, drug-induced hepatitis that resolved without evidence of hepatic failure would not be considered life-threatening even though drug-induced hepatitis can be fatal.

- c. Requires hospitalization or prolongation of existing hospitalization;

NOTE: In general, hospitalization signifies that the patient has been detained at the hospital or emergency ward for observation and/or treatment that would not have been appropriate in the physician’s office or out-patient setting. Complications that occur during hospitalization are adverse events. If a complication prolongs hospitalization or fulfills any other serious criteria, the event is serious. When in doubt as to whether “hospitalization” occurred or was necessary, the adverse event should be considered serious. Hospitalization for elective treatment of a pre-existing condition that did not worsen from baseline is not considered an adverse event.

- d. Results in persistent or significant disability/incapacity;

NOTE: The term disability means a substantial disruption of a person’s ability to conduct normal life functions. This definition is not intended to include experiences of relatively minor medical significance such as uncomplicated headache, nausea, vomiting, diarrhea, influenza, and accidental trauma (eg, sprained ankle) that may interfere or prevent everyday life functions but do not constitute a substantial disruption.

- e. Is a congenital anomaly/birth defect;

- f. Important medical events that jeopardize the patient and may require medical or surgical intervention to prevent one of the outcomes listed above. Examples of such events are invasive or malignant cancers, intensive treatment in an emergency room or at home for allergic bronchospasm, blood dyscrasias or convulsions that do not result in hospitalization, or development of drug dependency or drug abuse.

7.2. Adverse Event Reporting

The reporting of serious adverse events by the sponsor (Myovant Sciences GmbH) to regulatory authorities is a requirement and each authority has a timetable for reporting these events based upon established criteria. Likewise, it is the responsibility of the investigator to report serious adverse events to their local IRB/IEC.

Care will be taken not to introduce bias when detecting adverse events and/or serious adverse events. Open-ended and non-leading verbal questioning of the patient is the preferred method to inquire about adverse event occurrence. Appropriate questions include:

- “How are you feeling?”
- “Have you had any (other) medical problems since your last visit/contact?”
- “Have you taken any new medicines, other than those provided in this study, since your last visit/contact?”

The patient’s answers to the EQ-5D-5L will not be used as a primary means to collect adverse events, however they should be reviewed by the study site personnel and the study monitors. Should the investigator or site staff become aware of a potential adverse event through the information collected with these instruments, proper follow-up with the patient for medical evaluation should be undertaken. Through this follow-up, if it is determined that an adverse event not previously reported has been identified, normal reporting requirements should be applied.

All patients who experience an adverse event will be evaluated at appropriate time intervals until the event resolves or has stabilized or become chronic. At the conclusion of the study, the investigator and medical monitor will assess unresolved adverse events and determine if additional follow-up is warranted.

All adverse events, whether or not related to the study drug treatment, must be fully and completely documented on the adverse event case report form and in the patient’s source documents. In addition, any adverse event resulting in permanent treatment discontinuation must be recorded on the appropriate case report form as well as documented in the patient’s source documents. Adverse event terms should include a diagnosis, as available, in preference to listing the individual signs and symptoms. If the diagnosis is not known, the investigator should record each sign and symptom as an individual adverse event.

Overdose and pregnancy in a partner will be reported as described in Section 7.7 and Section 7.8, respectively.

7.2.1. Adverse Event Reporting Period

Adverse events will be collected from the time the first dose of study drug is administered until the Safety Follow-up visit approximately 30 days after the last dose of relugolix or 12 weeks plus 30 days after the last leuprolide acetate injection, or the date of initiation of another investigational agent or hormonal therapy or surgical intervention, whichever occurs first.

Serious adverse events will be collected from the signing of the informed consent form until the Safety Follow-up visit approximately 30 days after the last dose of relugolix or 12 weeks plus 30 days after the last leuprolide acetate injection, or the date of initiation of another

investigational agent or hormonal therapy or surgical intervention, whichever occurs first. Serious adverse events reported to the investigator after the safety reporting period should be reported to the sponsor if the investigator assesses the event as related to the study drug treatment.

Any event occurring between signing of the informed consent form and the first dose of study drug will be recorded as medical history and in the patient's clinical record for any patient who continues to meet eligibility criteria and proceeds to dosing with study drug; the exception to this includes procedure-related pretreatment-emergent events which should be recorded as adverse events in the electronic data capture (EDC) system for those patients who remain eligible for study participation.

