Hematology	X	X						X		X		X		X	X ^r	X			
Chemistry	X	X				X		X		X		X		X	X ^r	X			
Lipid & HbA1c ^k	X								X					X	X ^r	X			
PSA	X	X	X	X	X	X	X	X	X	X	X	X	X	X	X ^r	X	X	X	
Serum Testosterone	X	X	X	X	X	X ^l	X ^r	X	X	X									
LH/FSH		X	X			X				X				X	X ^r	X	X	X	
SHBG/DHT		X			X				X				X	X ^r				X	

Period	Screening Visit	Treatment Period Visits															Follow-up ^{a,c}		
		Safety ^b		Testosterone Recovery															
Visit Name	Screening	Baseline Day 1	Day 4	Wk 2 ^a	Wk 3	Wk 5	Wk 9	Wk 13	Wk 17 and 21	Wk 25	Wk 29 and 33	Wk 37	Wk 41 and 45	Wk 49 ^e	Un-scheduled	30-Day	60-Day	90-Day	
Study Day	-28 to -1	1	4	8	15	29	57	85	113 and 141	169	197 and 225	253	281 and 309	337		EOT + 30 days	EOT + 60 days	EOT + 90 days	
Visit Window	Not applicable	±2 days				± 7 days										± 7 days			
Blood Sample for Relugolix PK ^{m,n}		X ^{m,n}	X ⁿ	X ⁿ		X ^m	X ^r												
Blood Sample for DNA ^o		X														X ^r			
Health Status Survey ^p															X	X ^r			

Abbreviations: 3-M, 3-month; BMI, body mass index; CT, computed tomography; DHT, dihydrotestosterone; DNA, deoxyribonucleic acid; ECG, electrocardiogram; ECOG, Eastern Cooperative Oncology Group; EORTC, European Organization for Research and Treatment of Cancer; EOT, end of treatment; EuroQol EQ-5D-5L, European Quality of Life 5-Dimension 5-Level; FSH, follicle-stimulating hormone; HbA1c, hemoglobin A1c; LH, luteinizing hormone; MRI, magnetic resonance imaging; PK, pharmacokinetics; PSA, prostate-specific antigen; SHBG, sex hormone binding globulin

- The study day in which the Follow-up visit occurs is not specified in the table because these visits occur relative to when the patient takes his last dose of study drug. The End of Treatment (EOT) is defined as the last dose of relugolix or 12 weeks after the last leuprolide acetate injection.
- May occur earlier for patients who are starting alternative androgen deprivation therapy, or do not complete 12 weeks of study treatment. Adverse events, serious adverse events, and concomitant medications should continue to be collected and recorded through 30 days after the End of Treatment. All other study procedures should be completed before the start of alternative androgen deprivation therapy.

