5.4. Directions for Administration

Relugolix

Relugolix 120-mg tablet strength will be available as immediate-release film-coated tablets. These tablets will be presented in 45-tablet bottle packaging and dispensed to patients every 4 weeks at scheduled study visits.

All protocol-specific criteria for administration of study drug must be met and documented prior to study drug administration. Study drug will be dispensed by study personnel only to eligible patients who are under the supervision of the investigator or identified subinvestigator(s). If a blood draw or any study procedure coincides with a meal, the study procedure will take precedence, followed by the blood draw, and then the meal.

At the Baseline Day 1 visit, the site will administer a single loading dose of oral relugolix 360 mg (3 tablets).

Patients randomized to relugolix will be instructed to take one tablet on an empty stomach at least 1 hour before breakfast once daily. If the dose is missed in the morning for any reason, the study treatment may be taken later in the day, under fasting conditions, at least 1 hour before or 2 hours after eating a meal. The study treatment should be taken as close as possible to the same time of morning each day.

Patients may consume water ad libitum. Patients should swallow the study medication whole and not chew it or manipulate it in any way before swallowing.

Patients will hold their study treatment on clinic visit days and record the time of their previous dose (ie, the time that they took their dose on the day before the clinic visit); they will be instructed to take their study treatment in the clinic after PK and pharmacodynamic samples are collected.

Leuprolide Acetate

Leuprolide acetate 3-M depot injection, 22.5 mg (or 11.25 mg in Japan, Taiwan, and China), will be administered every 12 weeks. Leuprolide acetate 3-M depot will be administered on Day 1 at the clinic, then at 12-week intervals (see Schedule of Activities, Section 1.1) and investigators should follow product instructions provided by the manufacturer. An antiandrogen may be administered for the first 4 weeks or longer if indicated, as determined by the investigator, and/or as indicated by disease status (eg, in patients with extensive localized symptomatic disease or with metastatic disease).

Possible antiandrogen options include, but are not limited to, bicalutamide, flutamide, and nilutamide.

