5.10.2. Permitted Medications

All concomitant medications used during the study will be recorded. At a minimum, the drug generic name, dose amount, route of administration, start date, and stop date will be recorded in the source documents and the eCRF.

If alternative androgen deprivation therapy is initiated prior to 30 days after the last relugolix dose, record the alternative androgen deprivation therapy as a concomitant medication.

Patients with disease progression during the treatment period, in the setting of testosterone suppression to castrate levels (≤ 50 ng/dL [1.7 nmol/L]), should be encouraged to remain on study and, if indicated, may receive radiotherapy as prescribed by the investigator. In the setting of rising PSA patients may also receive enzalutamide after the confirmation of PSA progression. For patients requiring other systemic antineoplastic therapy during the treatment period, the investigator should contact the medical monitor.

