6.4. Follow-up Period

The study day in which the Follow-up visit occurs is relative to when the patient takes his last dose of study drug. The End of Treatment is defined as the last dose of relugolix or 12 weeks after the last leuprolide acetate injection.

30-Day Safety Follow-up Visit (Visit Window ± 7 Days)

A Safety Follow-up visit should occur 30 days after the End of Treatment and may occur earlier for patients who are starting alternative androgen deprivation therapy or do not complete 12 weeks of study treatment. Adverse events should continue to be collected and recorded through 30 days after the last dose of study drug or the date of initiation of another investigational agent or hormonal therapy or surgical intervention, whichever occurs first. Serious adverse events and concomitant medications will be collected from the signing of the informed consent form until the Safety Follow-up visit approximately 30 days after the last dose of study drug.

All other study procedures should be completed before the start of alternative androgen deprivation therapy.

The following assessments will be performed:

- Patient-reported questionnaires
 - Patients will complete the questionnaires on the tablet provided before other study procedures, such as blood draws and physical examinations, are performed;
- Vital signs and weight;
- 12-lead ECG;
- ECOG performance assessment;
- Symptom-based physical examination;
- Laboratory collection (see Section 1.1); and
- Concomitant medications and adverse events.

Testosterone Recovery Visit (Visit Window ± 7 Days)

Patients who have started alternative androgen deprivation therapy will not participate in the 60- and 90-day follow-up visits. Approximately 100 patients randomized to receive relugolix and approximately 50 patients randomized to receive leuprolide acetate who complete the 48 weeks of study drug treatment and, in the opinion of the investigator, are candidates for intermittent androgen deprivation therapy will be included in the Testosterone Recovery 60- and 90-day Follow-up visits. These patients will discontinue relugolix after 48 weeks of treatment and will be offered a period off androgen deprivation therapy.

The following assessments will be performed:

- Patient-reported outcome questionnaires
 - Patients will complete the questionnaires on the tablet provided before other study procedures, such as blood draws and physical examinations, are performed;
- Vital signs;

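### The protocol's rules on when adverse-event collection ends contradict one another and the treatment-emergent window; read literally, some stop it while men are still under treatment

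*Protocol*

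**What the plan says.** The protocol sets the end of collection in several places.

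- **Section 7.2.1** collects AEs and SAEs until the safety visit, which it times at about "30 days after the last dose of relugolix or 12 weeks plus 30 days after the last leuprolide acetate injection". It then adds an earlier stop for men who begin something new: "or the date of initiation of another investigational agent or hormonal therapy or surgical intervention, whichever occurs first".
- **Table 1-1 footnote j** gives the same limits, including the new-therapy stop, for serious and non-serious events.
- **Section 6.4**, on AEs: "Adverse events should continue to be collected and recorded through 30 days after the last dose of study drug". The same new-therapy stop follows. On SAEs: "until the Safety Follow-up visit approximately 30 days after the last dose of study drug", with no new-therapy stop. The section also states: "The End of Treatment is defined as the last dose of relugolix or 12 weeks after the last leuprolide acetate injection", and it sets the safety visit 30 days after that.
- **Table 1-1 footnote b**: "Adverse events, serious adverse events, and concomitant medications should continue to be collected and recorded through 30 days after the End of Treatment". It has no new-therapy stop.
- **Table 1-1 visit grid and Section 6.3** schedule AE assessment at every treatment visit in both arms.
- **Synopsis, Statistical Methods (Safety)** runs the treatment-emergent period to 30 days after the last relugolix dose, or 12 weeks plus 30 days after the last leuprolide dose. It has no new-therapy stop.

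Two hormonal therapies are allowed on study. In the leuprolide arm (Section 5.4): "An antiandrogen may be administered for the first 4 weeks or longer if indicated, as determined by the investigator". In both arms (Section 5.10.2): "In the setting of rising PSA patients may also receive enzalutamide after the confirmation of PSA progression". Men with progression are encouraged to stay on study.

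**The concern.** Section 7.2.1 and footnote j do not confine the new-therapy stop to the period after treatment. On the protocol's own terms an antiandrogen is another hormonal therapy: exclusion criterion 2 lists it as a form of androgen deprivation, and Section 5.1 defines study treatment as relugolix or leuprolide only. Taken literally, starting permitted therapy ends AE and SAE collection in a man who is still being treated. The antiandrogen route exists in the leuprolide arm only. The shorter limit in Section 6.4 also affects that arm only.

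Safety is summarised as the number and percentage of patients with events over the treatment-emergent period. Time inside that period in which sites were told not to record events would count as event-free. A later analysis plan cannot recover events that were never collected.

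**Working it through.** No sample-size formula applies. The check is day arithmetic and a comparison of passages.

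**Inputs**
- Last leuprolide injection: Week 37 visit, Study Day 253 (Synopsis, Table 1-1).
- Last relugolix dose: 48 weeks × 7 = Day 336.
- Week 49 visit: Day 337. Twelve weeks = 84 days.
- Leuprolide arm in the primary-analysis cohort: 305 men (Section 9.9).

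**1. Section 7.2.1 with no other therapy**
- Leuprolide: 253 + 84 + 30 = Day 367. This equals End of Treatment (253 + 84 = Day 337) plus 30.
- Relugolix: 336 + 30 = Day 366.
- The arms agree to within one day, and both match the treatment-emergent window.

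**2. Section 6.4 AE and SAE sentences, with the last dose read as the Week 37 injection**
- Leuprolide: 253 + 30 = Day 283. Relugolix stays at Day 366.
- Difference from Section 7.2.1: 367 − 283 = 84 days, and 84/367 = 22.9%.
- Day 283 is 337 − 283 = 54 days before the Week 49 visit. Week 45 (Day 309), Week 49 (Day 337) and the 30-day visit all fall after it.
- Ceiling for the arm: 305 × 84/365 = 70 patient-years. This needs every man to be followed to his Section 7.2.1 limit and every site to apply Section 6.4 instead.

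**3. New-therapy stop read literally**
- Antiandrogen on Day 1 (leuprolide only): 367 − 1 = 366 of 367 days lost.
- Enzalutamide on Day 169 (an assumed date, either arm): 367 − 169 = 198 days (54%) on leuprolide and 366 − 169 = 197 days (54%) on relugolix.
- Uptake is not stated. If a share f of the leuprolide arm starts an antiandrogen on Day 1, the share of that arm's collection time lost is f × 366/367. That is about 5% for f = 5%, 20% for f = 20% and 50% for f = 50%.

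**4. The rules side by side**

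| Passage | Keeps the 12 leuprolide weeks | Stops at new hormonal therapy |
|---|---|---|
| 7.2.1 (AE, SAE) | yes | yes |
| Footnote j (AE, SAE) | yes | yes |
| 6.4, AE sentence | no | yes |
| 6.4, SAE sentence | no | no |
| Footnote b (AE, SAE) | yes, through End of Treatment | no |
| Treatment-emergent definition | yes | no |

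No single practice at a site satisfies every row.

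**The case against.** The strongest reply is that sites would not apply the literal stop. The visit grid and Section 6.3 call for AE assessment at every visit in both arms, including Weeks 45 and 49, whatever other therapy a man takes. Section 6.4 concerns the follow-up period, defines End of Treatment as injection plus 12 weeks and places the safety visit 30 days later, so its reference to the last dose may be loose shorthand. Footnote b and Sections 4.7 and 6.4 all discuss men starting alternative androgen deprivation around or after the end of treatment, and the cut-off was probably meant for them. The antiandrogen is also described as part of leuprolide-arm administration. SAEs judged related are still reported after the period closes, and the SAE sentence in Section 6.4 has no new-therapy stop.

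Much of this stands: it shows that early truncation is not certain. It does not remove the contradiction. No passage limits the cut-off to the time after End of Treatment or exempts permitted therapy. The AE row of the visit grid itself carries footnote j, so the grid does not clearly override the stop. The backstop for late events covers only SAEs that the investigator judges related, in an open-label trial. It does not cover non-serious events or SAEs judged unrelated.

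**Conclusion.** The collection rules are wrong as written. They conflict with one another and with the treatment-emergent window. If sites follow the literal stops, up to 84 of 367 days (23%) is lost under Section 6.4 for a man who completes leuprolide, and more under Section 7.2.1 for a man given an antiandrogen early. These are upper bounds. They rest on reading the last dose as the Week 37 injection, on treating permitted antiandrogens as another hormonal therapy, and on sites choosing those passages over the others.

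A reader might infer more: that the plan does truncate safety follow-up unequally and bias the comparison, that men on an antiandrogen have no follow-up, or that 70 patient-years will be lost. The documents do not support this. AE assessment is scheduled at every visit, Section 6.4 also contains the longer limit through its End of Treatment definition, and antiandrogen uptake is not given. Enzalutamide is allowed in both arms, so the size and direction of any imbalance from it are unknown. What is established is a contradiction that sites could resolve either way, and some of those readings lose events inside the analysis window, more so in the leuprolide arm.

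**What to change.** Reconcile Section 6.4, Section 7.2.1 and Table 1-1 footnotes b and j to one rule:

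- Collect AEs and SAEs through 30 days after End of Treatment, using the definition the protocol already gives for each arm.
- Apply any cut-off at a new agent, hormonal therapy or surgery only after End of Treatment.
- State that antiandrogen, enzalutamide or procedures permitted on study do not end collection.

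This changes data collection only; no dose or treatment rule is touched. The cost is wording in four places, a memo to sites and slightly more AE recording.
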